6.3 SUBJECT SETS ANALYSED

All analyses will be performed on the Treated Set, as defined in Section 7.3 of the CTP, including patients coming from SENCIS and 1199.340.

Patients will be analysed according to their randomised treatment group in the parent trial (placebo or nintedanib) and overall (Total column). Patients from 1199.340 will be combined with placebo patients from SENCIS in the outputs, due to their short exposure to nintedanib during 1199.340. Patients in the placebo column are those who initiated nintedanib in the extension study, whilst patients in the nintedanib column are those who continued nintedanib.

The column of main interest in the tables will be the total column (includes both treatment groups) as all patients are treated with nintedanib during the extension study.

In addition, a selected set of analyses will be repeated in patients coming from SENSICIS only (see [Section 9.6](#) for further details) and in patients with pulmonary hypertension at baseline (see [Section 9.7](#) for further details).

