### 3.3 SELECTION OF TRIAL POPULATION

It is anticipated that approximately 400 patients will complete the SENSISCIS® trial on treatment with nintedanib or placebo and that approximately 14 patients will complete the 1199-0340 trial. These patients will be allowed to participate in this open label extension trial. At the time point of the start of the open label extension trial it is not known what treatment the patients had received in SENSISCIS®. Patients previously on active treatment will continue, patients who received placebo will initiate treatment with nintedanib for the first time at Visit 2 of the extension trial. Patients who completed 1199-0340 had open-label treatment with nintedanib and will continue with nintedanib treatment in 1199.225.

A log of all patients enrolled into the trial (i.e. who have signed informed consent) will be maintained in the ISF at the investigational site irrespective of whether they have been treated with investigational drug or not.

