#### 4.1.2 Method of assigning patients to treatment groups and selection of dose

The objective of the SENSISCIS® was to assess the efficacy and safety of a dose of 150 mg bid compared to placebo. Patients have been randomized either to blinded Nintedanib or to blinded placebo 150 mg bid. Dose reductions from 150 mg bid Nintedanib/placebo to 100mg bid Nintedanib/placebo were allowed to manage adverse events.

The objective of the trial 1199-0340 was to assess the potential influence of continuous intake of nintedanib on the systemic exposure of ethinylestradiol and levonorgestrel when administered in combination. The patients have all been treated with open label nintedanib. Also in trial 1199-0340 dose reductions from 150 mg bid nintedanib to 100mg bid nintedanib were allowed to manage adverse events.

Patients having taken 150 mg bid trial medication (active drug or placebo, blinded in SENSISCIS®) at the end of SENSISCIS® / 1199-0340 will start treatment with nintedanib 150 mg bid in the current extension trial.

Patients who receive 100 mg bid active drug or placebo within SENSISCIS® / 1199-0340 will be allowed to start treatment with 100 mg or increase their nintedanib dose to 150 mg bid at the discretion of the investigator.

Interactive Response Technology (IRT) will be used to assign medication numbers to eligible patients. Distribution of nintedanib to sites will be triggered by IRT. Details on the IRT system are provided in the ISF.

After subsequent conclusions on benefit/risk upon unblinded data from SENSISCIS®, patients who permanently reduced to 100 mg bid will be allowed to increase their nintedanib dose to 150 mg bid at the discretion of the investigator. Dose increase will need to be assigned through IRT during an additional visit (refer to [Section 6.2.4](#)).

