### 7.3 PLANNED ANALYSES

The treated set (TS) will consist of all patients who received at least one dose of open-label trial medication.

The definition of important protocol violations (IPV) will be specified in the trial statistical analysis plan (TSAP). These IPV definitions will include consideration of important violations of entry criteria, treatment non-compliance, restricted medications and inadequate follow-up of hepatic events.

Patients will be analysed according to their randomized treatment group in the previous trial SENCIS® / 1199-0340.

The last available value between Visit 1 and Visit 2 (before first trial drug intake) will be considered as the baseline, for this extension trial.

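### Does SAP 6.3 mislead by describing the pooled placebo column as first-time nintedanib users when it also holds the 1199.340 patients?

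*SAP*

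**What the plan says.** Protocol 7.3 sets the grouping rule: "Patients will be analysed according to their randomized treatment group in the previous trial", naming both parent trials. The documents describe no randomised groups in 1199-0340, so the SAP had to decide where its patients go.

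SAP 6.3 shows two columns by parent-trial treatment (placebo, nintedanib) plus a Total. It combines the 1199.340 patients with SENSCIS placebo and gives the reason: "due to their short exposure to nintedanib during 1199.340". The next sentence describes the columns: "Patients in the placebo column are those who initiated nintedanib in the extension study", while the nintedanib column holds those who continued. SAP 6.3 then adds: "The column of main interest in the tables will be the total column". SAP 3, 6.3 and 7 also provide for a repeat of selected analyses in SENSCIS patients only.

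On prior treatment, Protocol 3.3 says that "patients who received placebo will initiate treatment with nintedanib for the first time at Visit 2 of the extension trial", whereas "Patients who completed 1199-0340 had open-label treatment with nintedanib and will continue with nintedanib treatment in 1199.225". Protocol 4.1.2 confirms for 1199-0340: "The patients have all been treated with open label nintedanib".

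**The concern.** Taken alone, the SAP's description of the column contradicts the protocol. By its own split between initiating and continuing, the 1199.340 patients are continuers, and exclusion criterion 8 allows them at most one week between last intake and Visit 2.

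The distinction has content. Protocol 1.4 ties the close monitoring of the first three months to placebo patients receiving active drug for the first time. Several by-group outputs concern early onset: Kaplan-Meier plots of dose reduction, interruption and discontinuation (SAP 7.7), time to first liver enzyme elevation (SAP 7.8.2.2) and incidence rates with time at risk counted from first extension intake (SAP 7.8.1.5). For the 1199.340 patients that clock does not start at first exposure:

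- Adverse events still ongoing from 1199-0340, possibly begun on nintedanib, are entered as baseline conditions and count only if they worsen (Protocol 6.2.1 and 7.3.4).
- Dose reductions could already have happened: "Also in trial 1199-0340 dose reductions from 150 mg bid nintedanib to 100mg bid nintedanib were allowed to manage adverse events".
- To enter, they had to complete 1199-0340 without permanently stopping treatment (inclusion criterion 1), so they had already shown some tolerance of the drug.

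A reader who took the column as pure first-exposure data would be slightly wrong about what it contains.

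**Working it through.** **The two sentences together.** Within SAP 6.3, one sentence says that patients with short nintedanib exposure are put in the placebo column. The next says that everyone in that column starts nintedanib in the extension. The second cannot hold without exception if the first is true. Anyone who reads the paragraph sees both, so the second is shorthand for the bulk of the column.

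**Inputs.** About 400 SENSCIS completers and about 14 from 1199-0340 (Protocol 3.1). The documents give neither the SENSCIS allocation ratio nor the placebo share of entrants. I assume 50%, with a range of 40% to 60%. There is no figure in the plan to reproduce.

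**Share of the column.** Share = 14 / (placebo share × SENSCIS entrants + 14).

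| SENSCIS entrants | 40% placebo | 50% placebo | 60% placebo |
|---|---|---|---|
| 400 | 14/174 = 8.0% | 14/214 = 6.5% | 14/254 = 5.5% |
| 386 (synopsis total of 400 includes the 14) | 14/168.4 = 8.3% | 14/207 = 6.8% | 14/245.6 = 5.7% |
| 300 (fewer roll over, all 14 enter) | 14/134 = 10.4% | 14/164 = 8.5% | 14/194 = 7.2% |

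**Effect on a patient percentage.** Pooled % − true-initiator % = share × (1199.340 % − true-initiator %). The difference needed to move the column by one point is 1/share:

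- 400 entrants, 50% placebo: 1/0.0654 = 15.3 points
- 400 entrants, 40% placebo: 1/0.0805 = 12.4 points
- 400 entrants, 60% placebo: 1/0.0551 = 18.1 points
- 300 entrants, 40% placebo: 1/0.1045 = 9.6 points

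This identity holds for percentages of patients only. Incidence rates per 100 patient-years weight by time at risk, and Kaplan-Meier quartiles are not proportions, so it does not bound those. No event rates, exposure durations or counts of earlier dose reductions are given for 1199.340, so no shift can be estimated for any output.

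**Effect on Total.** Total holds all treated patients whichever column they sit in. Its numerator, denominator and time at risk change by 0.

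**Other placements.** Moving the 14 to the nintedanib column would make the word for continuing true, but would mix short prior exposure with that of patients who completed SENSCIS on nintedanib. At an even split they would be the same 14/214 = 6.5% of that column. Showing them only in Total would leave 14/414 = 3.4% of patients outside both columns, so the columns would no longer add up to Total. Neither is clearly better than what the SAP chose.

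**The case for a change.** The strongest case for acting is that the sentence is plainly false for an identifiable group, that in a purely descriptive trial accurate group definitions are what readers rely on, and that correcting it would cost almost nothing. One planned table shows the mixture directly: SAP 7.7 sets dose at inclusion against dose at the end of the parent trial by parent group, and in the pooled column the parent dose was placebo for some patients and active drug for others. The SENSCIS-only repeat covers selected analyses, and its list (SAP 9.6) is not in the supplied text, so one cannot confirm that it includes the early-onset outputs.

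The inaccuracy stands, and so does the point that this column is not a clean first-exposure group. The rest carries less weight. The SAP tells the reader about the prior exposure immediately before the loose sentence, and rewording would not alter any computed number. Starting the clock at first extension intake is the stated scope of the exposure and time-at-risk analyses and applies equally to every SENSCIS nintedanib patient, so pooling does not cause it. Carried-over events and earlier dose reductions are possibilities without counts. The SAP 7.7 table by entry dose would make entry on a reduced dose visible. The missing list is a limit of the supplied text and cannot be held against the plan.

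**Conclusion.** The sentence in SAP 6.3 is a drafting slip and does not call for a change to the plan. The pooling itself is disclosed, reasoned and defensible for a small group with no randomised arm to follow. The primary endpoint is overall adverse event incidence, no hypothesis is tested, and the column of main interest is unaffected. Readers who want strictly first-exposure results can look to the planned SENSCIS-only repeat.

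The affected share is about 6.5% of one descriptive column, with a range of about 5.5% to 10.4% over an assumed 40% to 60% placebo share and 300 to 400 SENSCIS entrants, with all 14 patients from 1199.340 entering. Limiting the by-group columns to SENSCIS patients would undo a deliberate choice and leave columns that do not sum to Total, for an effect of unknown size and direction. That is a preference between acceptable layouts and brings no demonstrated gain.

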6.5 POOLING OF CENTRES

This section is not applicable because centre/country is not included in a statistical model.

6.6 HANDLING OF MISSING DATA AND OUTLIERS

6.6.2 Other endpoints

6.6.2.1 Concomitant therapies

In case of (partially) missing start and end dates of concomitant therapies, the dates will be imputed so that the extent of exposure to the concomitant therapy is maximal, i.e. the first day (month) of the month (year) for incomplete start dates and the last day (month) of the month (year) for incomplete end dates.

6.6.2.2 Safety endpoints

Missing or incomplete AE dates will be imputed according to BI standards (see “Handling of missing and incomplete AE dates”) (2).

6.7 BASELINE, TIME WINDOWS AND CALCULATED VISITS

As a general rule, the last assessment/measurement before the date of first trial drug intake (included) will be used as baseline (possibly Visit 1 assessment if no available value at Visit 2).

Visit windowing will be performed as described in [Tables 6.7: 1](#), [6.7: 2](#) and [6.7: 3](#), in order to assign data to the relevant study visit based on the actual day of the assessment. Data will be analysed using the re-calculated visits in the statistical tables. However, in the listings, all visits performed will be displayed (even if outside time-window), along with the re-calculated visit. No time-windowing will be performed for the follow-up visit (all follow-up visits will be displayed in the tables / listings whenever they were performed).

Table 6.7: 1 Time windowing rules for [REDACTED] physical exam, vital signs and laboratory measurements (haematology, coagulation, biochemistry – CK, glucose non-fasting, LDH, uric acid, HCG)

Time window of actual day ^[1]			Allocated to		
Start day	End day (included)	Length of the time-window [days]	Visit number	Visit name	Planned day of the visit
1	1	1	1 or 2 ^[2]	Baseline	1
2	57	56	3	4 weeks	29
58	127	70	4	12 weeks	85
128	211	84	5	24 weeks	169
212	309	98	6	36 weeks	253
310	421	112	7	52 weeks	365
422	533	112	8	68 weeks	477
534	645	112	9 _(p)	Every 16 weeks thereafter	589 (V_p)
$V_p + 1 + (V_{p+1} - V_p)/2$	$V_{p+1} + (V_{p+2} - V_{p+1})/2$	$(V_{p+2} - V_p)/2$	p+1	...	V_{p+1}

[REDACTED]
 V_p denotes the planned day of the visit

[1] First trial drug intake date in extension trial is taken into account as a reference to calculate time windows

[2] Depending on the last assessment before first trial drug intake (included), refer to [Section 6.7](#) for baseline definition

Table 6.7: 2 Time windowing rules for [REDACTED] laboratory measurements (biochemistry - BNP, TSH)

Time window of actual day ^[1]			Allocated to		
Start day	End day (included)	Length of the time-window [days]	Visit number	Visit name	Planned day of the visit
1	1	1	2	Baseline	1
2	267	266	5	24 weeks	169
268	421	154	7	52 weeks	365
422	533	112	8 (p)	Every 16 weeks thereafter	477 (V_p)
$V_p + 1 + (V_{p+1} - V_p)/2$	$V_{p+1} + (V_{p+2} - V_{p+1})/2$	$(V_{p+2} - V_p)/2$	p +1	...	V_p +1

V_p denotes the planned day of the visit

[1] First trial drug intake date in extension trial is taken into account as a reference to calculate time windows

Table 6.7: 3 Time windowing rules for laboratory measurements (electrolytes, urinalysis, urine pregnancy test, biochemistry – AST, ALT, GGT, ALK, total protein, total bilirubin, creatinine, GFR)

Time window of actual day ^[1]			Allocated to		
Start day	End day (included)	Length of the time-window [days]	Visit number	Visit name	Planned day of the visit
1	1	1	1 or 2 ^[2]	Baseline	1
2	22	21	2a	2 weeks	15
23	43	21	3	4 weeks	29
44	71	28	3a	8 weeks	57
72	106	35	4	12 weeks	85
107	148	42	4a	18 weeks	127

Table 6.7: 3 Time windowing rules for laboratory measurements (electrolytes, urinalysis, urine pregnancy test, biochemistry – AST, ALT, GGT, ALK, total protein, total bilirubin, creatinine, GFR) (cont'd)

Time window of actual day ^[1]			Allocated to		
Start day	End day (included)	Length of the time-window [days]	Visit number	Visit name	Planned day of the visit
149	190	42	5	24 weeks	169
191	232	42	5a	30 weeks	211
233	281	49	6	36 weeks	253
282	337	56	6a	44 weeks	309
338	393	56	7 _(p)	52 weeks	365 (V_p)
$V_p + 1 + (V_{p+1} - V_p)/2$	$V_{p+1} + (V_{p+2} - V_{p+1})/2$	$(V_{p+2} - V_p)/2$	p+1	Every 8 weeks	V_{p+1}

V_p denotes the planned day of the visit

[1] First trial drug intake date in extension trial is taken into account as a reference to calculate time windows

[2] Depending on the last assessment before first trial drug intake (included), refer to [Section 6.7](#) for baseline definition

7. PLANNED ANALYSIS

All analyses described in this section will be done on the Treated Set.

The list of analyses planned in patients coming from SENSCIS parent trial only is included in [Section 9.6](#).

For End-Of-Text tables, the set of summary statistics is: N / Mean / SD / Min / Median / Max. In descriptive statistics tables, mean, SD and median will be rounded to one additional digit than the raw individual value.

In case some endpoints show some extreme data, quartiles and percentiles will be presented additionally.

Tabulations of frequencies for categorical data will include all possible categories and will display the number of observations in a category as well as the percentage (%) relative to the respective treatment group (unless otherwise specified, all patients in the respective patient set whether they have non-missing values or not). Percentages will be rounded to one decimal place. The category missing will be displayed only if there are actually missing values.

7.1 DEMOGRAPHIC AND OTHER BASELINE CHARACTERISTICS

Only descriptive statistics are planned for this section of the report.

7.2 CONCOMITANT DISEASES AND MEDICATION

Only descriptive statistics are planned for this section of the report.

7.2.1 Baseline conditions

A summary of baseline conditions will be provided by randomised treatment group in parent trial (and overall), System Organ Class (SOC) and Preferred Term (PT). SOC and PT will be sorted by descending frequency (over the Total column).

7.2.2 Concomitant therapies

Concomitant therapies will be described over several study periods:

- Baseline therapies will be defined as treatments with a start date before first trial drug intake in extension trial and a stop date after or on the day of the first trial drug intake in extension trial (or ongoing after first trial drug intake in extension trial).
- On-treatment concomitant therapies are defined as treatments with a start date after or on the day of first trial drug intake in extension trial and before or on the day of last trial drug intake in extension trial.

- Post-study drug discontinuation therapies are defined as treatments with a start date after last trial drug intake in extension trial and before or on the last contact as collected in the end of study CRF page. This aims at flagging concomitant treatments taken by patients after they have stopped the study drug.

Table 7.2.2:1 summarises the concomitant therapy outputs which will be provided for each category of concomitant therapy created.

Summaries by ATC and preferred name (PN) will use the ATC3 code, and will be sorted by alphabetical ATC class and decreasing frequency of PN in the Total column within ATC class.

Summaries by Customised Drug Grouping (CDG) will be sorted alphabetically by the name of the CDG and by decreasing frequency of PN in the Total column within a CDG. CDGs are built using WHO-DD Standardised Drug Groupings (SDG), Sub-SDGs and ATC4 levels. CDGs are listed in [Section 9.3](#).

Table 7.2.2: 1 Concomitant therapy outputs and position in the CTR

	By ATC and PN	By CDG and PN
Baseline therapies	16.1.13.1	15.1
On-treatment concomitant therapies	16.1.13.1	16.1.13.1
All on-treatment concomitant therapies* with a frequency >2% (in the Total column)	16.1.13.1	Not required
All on-treatment concomitant therapies*	16.1.13.1	15.1
Post-study drug discontinuation therapies	Not required	16.1.13.1

* including baseline therapies.

7.3 TREATMENT COMPLIANCE

Only descriptive statistics are planned for this section of the report.

7.4 PRIMARY ENDPOINT(S)

The primary objective of the trial is to assess the safety of Nintedanib, so please refer to [Section 7.8](#) for detailed analyses.

7.5 SECONDARY ENDPOINT(S)

7.5.1 Key secondary endpoint(s)

This section is not applicable as no key secondary endpoint has been specified in the protocol.

7.5.2 (Other) Secondary endpoint(s)

This section is not applicable as no secondary endpoint has been specified in the protocol.

7.7 EXTENT OF EXPOSURE

A summary table showing the duration on treatment in extension trial (both mean and frequency in classes, see [Section 5.4.3](#)) will be presented as well as a summary table showing the duration on actual treatment dose (both mean and frequency in classes, see Section 5.4.3) and off-treatment duration. This will take into account the actual dose following dose reductions or increases.

A summary of treatment interruptions will be performed including number of patients with at least one interruption, number and reason of interruptions, as well as time to first interruption (both mean and frequency in classes, see Section 5.4.3). A similar summary will be performed for dose changes.

For the above mentioned analyses, data will be presented over 52 weeks, 100 weeks, 148 weeks as well as over the whole trial.

The proportion of patients on each dose actually taken at inclusion in 1199.225 will be displayed according to:

- the dose actually taken at the end of parent trial (by parent trial treatment group and all combined)
- last dose actually taken in 1199.225 extension trial

A table displaying the disposition of patients and the conclusion of patients' participation, and a table displaying the primary reason for non-inclusion will be provided.

A Kaplan-Meier plot of time to permanent treatment discontinuation will be produced. Similarly, Kaplan-Meier plots will be performed for time to first dose reduction, for time to first treatment interruption and for time to first dose reduction or treatment interruption. Plots will be done by randomised treatment group in parent trial and overall. The 25th, median and 75th percentiles derived from the Kaplan-Meier plots of these time-to-event endpoints will be presented as well. No statistical tests will be performed.

For all the above mentioned time to event endpoints, a summary table of time to first onset and number of patients with an event will be presented. The time to onset of first event [days] will also be summarised by categories : <= 1 month (30 days), > 1 month (30 days) to <= 2 months (61 days), > 2 months (61 days) to <= 3 months (91 days); > 3 months (91 days) to <= 6 months (182 days); > 6 months (182 days) to <= 1 year (365 days); > 1 year (365 days) to <= 2 years (730 days); > 2 years (730 days) to <=3 years (1095 days), > 3 years (1095 days).

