### 3. DESCRIPTION OF DESIGN AND TRIAL POPULATION

#### 3.1 OVERALL TRIAL DESIGN AND PLAN

This is a multi-centre, multi-national, prospective, open label extension clinical trial. It is anticipated that approximately 400 patients with SSc-ILD will complete the parent trial SENSISCIS® and approximately 14 patients will complete 1199-0340 as planned. These patients will be eligible for enrolment in this extension trial. Patients who withdrew treatment prematurely in SENSISCIS® / 1199-0340 will not be eligible for this open label extension trial.

After signing Informed Consent and if all eligibility criteria are met, patients will initiate treatment with nintedanib (Visit 2). Patients will be assigned to a dose of 150 mg bid if the patients last dose in SENSISCIS® / 1199-0340 was 150 mg bid and to a dose of either 100 mg bid or 150 mg bid at the discretion of the investigator, if patients were on 100 mg bid of blinded trial medication in SENSISCIS® / 1199-0340 (please refer to [Section 4.1.2](#)).

Once assessment of the pivotal trial SENSISCIS® and resulting risk-benefit of Nintedanib has been concluded upon, patients that are on a reduced dose of trial medication may increase dose to 150 mg bid Nintedanib at the discretion of the investigator.

The trial will continue for long term data collection, as long as a reasonable number of patients enabling analyses remain in the trial. Treatment duration for each patient will be variable. Patients will continue to receive treatment until they meet a reason for discontinuation (refer to [section 3.3.4.4](#)) or until access to nintedanib is obtained outside the clinical trial. The trial is estimated to last a total of approximately 5 ½ years.

Treatment will be stopped if a reason for withdrawal is met (refer to [Section 3.3.4](#)).

[figure not shown]

Figure 3.1: 1 Transition from parent trial SENSISCIS® / 1199-0340

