7.8.1.4 Adverse events of particular note

Gastro-intestinal adverse events (diarrhoea, nausea, vomiting, dehydration, weight decrease and decreased appetite) are considered as AEs of particular note.

Specific tables will be created in order to describe adverse events of particular note in the extension trial:

- Summary of AEs including intensity, seriousness, clinical consequences (permanent dose reduction, drug discontinuation or drug interruption), drug relationship, therapy for event and outcome
- Summary of AEs including time to onset, number and duration of episodes

In the summary of adverse events of particular note including intensity, seriousness, clinical consequences, drug relationship, therapy for event and outcome: for patients with several episodes, the worst intensity, relationship, outcome and clinical consequence during on-treatment period will be displayed. For clinical consequences, the worst category is

considered to be “Drug withdrawn”, then “Dose reduced”, “Dose not changed” and finally “Dose increased”. Worst to best outcome are: “Fatal”, “Recovered/Resolved with sequelae”, “Not Recovered/Not Resolved”, “Recovered/ Resolved”, “Unknown”.

Depending on the number of patients having such AEs, a Kaplan-Meier plot of time to first adverse event of particular note may be drawn by randomised treatment in parent trial (and Total).

In addition, for pairs of selected adverse events (from diarrhoea, nausea, vomiting, decreased appetite, dehydration, weight decreased as defined in (8)), the frequency of patients with concurrent AEs will be summarised by treatment where concurrence is defined as an overlap of at least one day.

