7.8.2.2 Liver enzyme and bilirubin elevations

Specific tables and graphs will be presented by randomised treatment in parent trial (and Total) to describe liver enzyme elevations as defined in [Section 5.4.4](#):

- Summary table of liver enzyme elevation including time to first onset and number of patients with liver enzyme elevation. The time to onset of first liver enzyme and bilirubin elevation [days] will be summarised by categories (≤ 30 days; >30 to ≤ 91 days; >91 to ≤ 182 days; >182 to ≤ 365 days; >365 to ≤ 547 days; >547 to ≤ 730 days, >730 to ≤ 1095 days, >1095 days).
- Kaplan-Meier plot of time to first liver enzyme elevation. No statistical test will be performed.
- Summary table of individual maximum liver enzyme and bilirubin elevations by time period (over 52 weeks, 100 weeks, 148 weeks and over the whole trial).
- Plot of time course profile of liver enzyme for patients having liver enzyme and bilirubin elevation.

Due to a change in the Central Laboratory analyzing samples between SENSISCIS and this extension trial, the proportion of patients with liver enzyme and bilirubin elevations according to the cut-offs defined in Section 5.4.4 and using the Upper Limit of Normal from the Central Laboratory from SENSISCIS will be described as well in CTR Appendix 16.1.13.1.

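### Kaplan-Meier curves and quartiles for first dose reduction and first interruption take no visible account of permanent discontinuation or death as competing events, so risks would read too high and quartile times too early

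*SAP*

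**What the plan says.** SAP 5.4.6 lists the safety time-to-event variables: first dose reduction, first interruption, the composite of these, permanent discontinuation, and first liver enzyme elevation.

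For the dosing variables, SAP 7.7 states that "Kaplan-Meier plots will be performed for time to first dose reduction, for time to first treatment interruption and for time to first dose reduction or" interruption, by parent-trial group and overall. It then states that "The 25th, median and 75th percentiles derived from the Kaplan-Meier plots of these time-to-event endpoints will be presented as well", and that "No statistical tests will be performed". Beside the curves, "a summary table of time to first onset and number of patients with an event will be presented", with onset grouped into time categories up to beyond 3 years.

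Two other places use the method. SAP 7.8.2.2 plans a "Kaplan-Meier plot of time to first liver enzyme elevation", and SAP 7.8.1.4 says that, depending on numbers, "a Kaplan-Meier plot of time to first adverse event of particular note may be drawn". Neither asks for percentiles.

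On follow-up, Protocol 3.1 says "Treatment duration for each patient will be variable". Treatment ends when a discontinuation reason is met or when the patient obtains nintedanib outside the trial. The same section puts the trial at about 5½ years, while the synopsis says about 34 months; these two need reconciling. The visible text gives no censoring or competing-event rule for the dosing endpoints. Parts of the SAP are redacted, so this point rests on the stated choice of Kaplan-Meier and not on something being absent.

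**The concern.** A first dose reduction or first interruption can occur only in a living patient who is still on nintedanib. Permanent discontinuation and death remove the possibility for good. Kaplan-Meier with those patients censored treats them as if they would have gone on to have the event at the rate of patients still treated. The result describes a population in which nobody stops or dies, not the patients in the trial.

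The assumption behind the censoring is also doubtful here. Protocol 4.2.1 says permanent discontinuation should be considered for severe effects at 150 mg bid, and Protocol 3.3.4.1 makes it mandatory for signs of hepatic injury. Some of the patients with the worst tolerability may therefore stop without a prior reduction and be censored as though at average risk.

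At stake is how the long-term tolerability results are read. A median time to first reduction is easily taken as the time by which half of the patients had reduced. With continuing attrition that may be untrue, and the discrepancy grows over the later years that the extension is meant to describe. If stopping rates differ between patients starting nintedanib and those continuing it, the distortion also differs between the displayed curves.

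**Working it through.** **Inputs.** The plan states no event rate, so there is no figure to reproduce. All hazards below are assumptions: first dose reduction λ = 0.20/year, and permanent stop or death without prior reduction μ = 0.10 or 0.20/year, both constant. The times 52, 100 and 148 weeks are the SAP's reporting periods (weeks divided by 52.18 to give years), and 5.5 years is from Protocol 3.1.

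**Formulas.** With stops and deaths censored:

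- 1 − KM(t) = 1 − exp(−λt)
- cumulative incidence CIF(t) = λ/(λ+μ) × [1 − exp(−(λ+μ)t)]

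**At 3 years.** 1 − exp(−0.6) = 45.1%. For μ = 0.10: (0.20/0.30) × [1 − exp(−0.9)] = 39.6%. For μ = 0.20: (0.20/0.40) × [1 − exp(−1.2)] = 34.9%.

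| Time | 1 − KM | CIF, μ = 0.10 | CIF, μ = 0.20 |
|---|---|---|---|
| 52 weeks | 18.1% | 17.2% | 16.4% |
| 100 weeks | 31.8% | 29.2% | 26.8% |
| 148 weeks | 43.3% | 38.2% | 33.9% |
| 3 years | 45.1% | 39.6% | 34.9% |
| 5.5 years | 66.7% | 53.9% | 44.5% |

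At the synopsis duration (34/12 = 2.83 years) the figures are, to one decimal, those of the 148-week row.

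**Quartile times.** Under Kaplan-Meier, t = −ln(1−p)/λ. Under the CIF, t = −ln[1 − p(λ+μ)/λ]/(λ+μ), which exists only if p(λ+μ)/λ < 1.

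| Percentile | KM | CIF, μ = 0.10 | CIF, μ = 0.20 |
|---|---|---|---|
| 25th | 1.44 y | 1.57 y | 1.73 y |
| Median | 3.47 y | 4.62 y | never reached |
| 75th | 6.93 y | never reached | never reached |

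The Kaplan-Meier times are too early, because an inflated curve crosses each threshold sooner.

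**Sensitivity to the hazards.** For λ from 0.05 to 0.50 and μ from 0.05 to 0.30/year, the excess of 1 − KM over the CIF is 0.1 to 4.9 points at 52 weeks, 0.9 to 19.7 at 148 weeks and 2.9 to 32.6 at 5.5 years.

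**Sensitivity to shape.** Take λ = 0.8/year for 6 months, then 0.08/year. The cumulative hazard at 3 years is 0.4 + 0.2 = 0.6, so 1 − KM is again 45.1%. The CIF is the sum of the two phases:

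- μ = 0.10: (0.8/0.9)[1 − exp(−0.45)] + exp(−0.45)(0.08/0.18)[1 − exp(−0.45)] = 32.2% + 10.3% = 42.5%
- μ = 0.20: 0.8[1 − exp(−0.5)] + exp(−0.5)(0.08/0.28)[1 − exp(−0.7)] = 31.5% + 8.7% = 40.2%

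The gap is about half that under constant hazards.

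**Simulation.** With 414 patients (400 + 14, Protocol 3.1), 1,000 runs and administrative censoring uniform over 4.0 to 5.5 years, mean 1 − KM at 4 years was 45.0% against an Aalen-Johansen estimate of 37.8% (λ = 0.15, μ = 0.10). For λ = 0.30, μ = 0.20 it was 70.0% against 52.0%, with mean estimated medians of 2.30 and 3.59 years.

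**The case against.** **The stakes are modest, and crude counts stand beside the curves.** No tests are planned on these curves, all analyses are descriptive, and the primary endpoint (number and percentage of patients with adverse events) uses no Kaplan-Meier. SAP 7.7 also tabulates patients with an event and summarises interruptions and dose changes over 52, 100 and 148 weeks and the whole trial. By the default in SAP 7, percentages use all patients in the group. Discontinuation has its own curve, so attrition is visible. All of this stands and keeps the point at the level of an improvement. It does not repair the quartiles: with variable, administratively censored follow-up, crude proportions are not estimates of risk by a given time.

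**Kaplan-Meier answers a legitimate question.** Risk while treatment continues is of interest, and cumulative incidence falls mechanically when more patients stop. This stands as a reason to keep the curve, provided that it is labelled as such.

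**The censoring rule is inferred, and the size is assumed.** Both stand. A redacted section could contain a rule. Exits to nintedanib outside the trial can reasonably be censored, so not all attrition adds to the excess.

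**A stronger reading does not hold.** A reader might infer that the liver and gastrointestinal plots share the fault in full. The documents do not support that. These events can occur after stopping; stopping matters only because the on-treatment window closes 7 days after last intake (SAP 6.1 and 7.8.1). Only death truly precludes them. No percentiles are planned there, and the gastrointestinal plot is optional.

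**Conclusion.** The point holds for the three dosing endpoints in SAP 7.7: first dose reduction, first interruption and their composite. If permanent stops and deaths are censored, as standard Kaplan-Meier does, the curve overstates the proportion affected and places the quartiles too early. The direction is certain once competing events occur; the size is not. Under the assumed constant hazards the excess is about 1 to 2 points at 52 weeks and about 5.5 to 10 points at 3 years, with the latter roughly halved if reductions are front-loaded. The 5.5-year figures depend most on the constant-hazard assumption and on which stated trial duration applies, so they should not be taken as a forecast.

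Kaplan-Meier for time to permanent discontinuation is not part of this point.

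**What to change.** In SAP 7.7, for the three dosing endpoints:

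- State the censoring and competing-event rules explicitly.
- Add Aalen-Johansen cumulative incidence at 52, 100 and 148 weeks and over the whole trial, by parent-trial group and overall, with the 25th, 50th and 75th percentiles given as 'not reached' where that is so.
- Treat death and non-administrative permanent discontinuation as competing events. Censor only administrative exits: nintedanib obtained outside the trial, and site or trial closure.
- Keep the Kaplan-Meier plots as supportive, labelled as hypothetical risk while treatment continues.

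For the liver plot in SAP 7.8.2.2 and the optional gastrointestinal plot in SAP 7.8.1.4, the same addition is optional.

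The cost is SAP wording and a standard SAS option. Reasons for withdrawal and discontinuation are already recorded in the eCRF (Protocol 3.3.4.3 and the end-of-treatment text in 6.2.2), so no new data are needed. The small downside is one more estimator to explain in the report.
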